6.4.1. Nonresponder Imputation

An NRI method imputes missing values as nonresponses and can be justified based on the composite strategy for handling intercurrent events (ICH E9 R1). This imputation procedure assumes the effects of treatment disappear after an occurrence of the intercurrent event (described in Section 6.4). For analyses which utilize censoring, randomized patients without at least 1 postbaseline observation will be defined as nonresponders for all visits. As well, patients who are missing a value prior to discontinuation or were rescued to a higher dose (if censoring on the latter) (ie, the patient is missing an intermediate visit) will be imputed as nonresponders on that visit only.

6.4.2. Mixed-Model for Repeated Measures

Mixed-model for repeated measures analyses will be performed on continuous endpoints to mitigate the impact of missing data. This approach assumes missing observations are missing at random (missingness is related to observed data) and borrows information from patients in the same treatment arm taking into account both the missingness of data through the correlation of the repeated measurements.

Essentially MMRM estimates the treatment effects had all patients remained on their initial treatment throughout the study. For this reason, the MMRM imputation implies a different estimand (hypothetical strategy [ICH E9 R1]) than the one used for NRI on categorical outcomes.

MMRM is executed after application of any censoring rules.

6.4.3. Modified Last Observation Carried Forward

An mLOCF imputation technique replaces missing data with the most recent nonmissing postbaseline assessment. The specific modification to the LOCF is data after an intercurrent event will not be carried forward thus the mLOCF is applied after the specified censoring rule is implemented. The mLOCF assumes the effect of treatment remain the same after the event that caused missing data as it was just prior to the missing data event. Analyses using mLOCF require a nonmissing baseline and at least 1 postbaseline measure otherwise the data is missing for analyses purposes. Analyses using mLOCF help ensure the number of randomized patients who were assessed postbaseline is maximized and is reasonable for this data as data directly prior to an intercurrent event (such as initiation of rescue therapy or drop out) is likely a nonefficacious response.

mLOCF will be used as the Primary analysis in/after February 2021 DBL, as NRI may underestimate potential treatment effect in a long-term study where patients drop out for multiple reasons. For period 1 and period 2 summary and analysis, mLOCF will be used as the primary analysis for all categorical endpoints (including PROs), and NRI will be used as sensitivity analysis.

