4.2. Secondary Objectives

The secondary objectives of this study are:

Objectives	Endpoints
Weeks 0-52	
Baricitinib Patients at Entry to Study JAHN To evaluate the effect of increasing or maintaining baricitinib dose on clinical measures and patient-reported outcomes.	
 Proportion of patients with a response of Investigator's Global Assessment (IGA) 0, 1, or 2 assessed at Weeks 16, 36, and 52 Proportion of patients with a response of IGA 0 or 1 assessed at Weeks 16, 36, and 52 (nonresponders) Proportion of patients achieving response of $\geq 75\%$ improvement from baseline in Eczema Area and Severity Index score (EASI75) from baseline of originating study assessed at Weeks 16, 36, and 52 Proportion of patients with a 4-point improvement from baseline of originating study in Itch Numeric Rating Scale (NRS) at Week 16
Placebo Nonresponders at Entry to Study JAHN To evaluate the effect of starting baricitinib 2-mg versus 4-mg on clinical measures and patient-reported outcomes.	
 Proportion of patients with a response of IGA 0, 1, or 2 assessed at Weeks 4, 16, 24, 52 Proportion of patients with a response of IGA 0 or 1 assessed at Weeks 4, 16, 24, 52 Proportion of patients achieving response of EASI75 from baseline of originating study assessed at Weeks 4, 16, 24, 52 Proportion of patients with a 4-point improvement from baseline of originating study in Itch NRS at Week 16

Objectives	Endpoints
Weeks 52-104	

All Patients Entering the Substudy To evaluate the change in clinical response after treatment withdrawal or downtitration.
 
Patients Entering the Substudy with IGA 0 or 1 To evaluate the change in clinical response after treatment withdrawal or downtitration.
	
 • Proportion of patients with a response of IGA 0, 1, or 2 assessed at 16 weeks after rerandomization (Week 68) and Week 104 • Proportion of patients with a response of IGA 0 or 1 assessed at 16 weeks after rerandomization (Week 68) and Week 104 • Proportion of patients with a response of EASI75 from baseline of originating study assessed at 16 weeks after rerandomization (Week 68) and Week 104 • Time to retreatment (time to IGA \geq3)

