6.1. Determination of Sample Size

It is anticipated that 95% of enrolled patients will complete Studies JAHL, JAHM, and JAIY and roll over into Study JAHN. Therefore, planned enrollment into Study JAHN from the originating Studies JAHL, JAHM, and JAIY will be approximately 1425 patients. Patients who are nonresponders at entry into Study JAHN and were not randomized to baricitinib 4 mg will be randomized 1:1 to either baricitinib 4 mg or baricitinib 2 mg and will be stratified by disease severity at baseline of JAHN (IGA 0, 1, and 2 versus IGA 3 versus IGA 4). This study is intended to evaluate patients' long-term response of baricitinib, and the sample sizes are not determined to detect differences between baricitinib and an appropriate comparator in a statistically powered manner. Additional patients may enroll from addenda or other studies.

Patients at Week 52 will be stratified by responder status (IGA 0 or 1 versus IGA 2) when entering the randomized withdrawal and downtitration substudy. It is estimated that there will be approximately 600 patients entering the randomized withdrawal and downtitration substudy. The substudy is meant to evaluate the change in clinical response after treatment withdrawal or downtitration and does not account for whether the sample size is sufficient to detect a difference between baricitinib and placebo. Maintenance of treatment benefit is defined as response of IGA 0, 1, or 2.

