6.4. Handling of Dropouts or Missing Data

Intercurrent events (ICH E9 R1) are events which occur after randomization such that subsequent data (collected after the intercurrent event) are difficult to interpret.

Depending on the estimand being addressed, different methods will be used to handle missing data as a result of intercurrent events. Intercurrent events can occur through the following:

- application of the censoring rule (including after permanent study drug discontinuation or for responders and partial responders [on Placebo or baricitinib 1-mg] who are rescued to a higher dose [baricitinib 2 mg or baricitinib 4 mg])
- retreatment after downtitration or early withdrawal
- discontinuation
- missing an intermediate visit prior to discontinuation or rescue
- lost to follow-up

Noncensor intercurrent events are events that are not due to the application of any censoring rule (ie, the last 3 items in the list above).

Note that as efficacy and health outcome data can accrue after a patient permanently discontinues study drug or is rescued to either baricitinib 2 mg or baricitinib 4 mg (for responders and partial responders on placebo or baricitinib 1 mg), a censoring rule will be applied to all efficacy and health outcome observations subsequent to these events depending on the estimand being addressed.

The *Period 1 censoring rule* will censor efficacy after permanent study drug discontinuation or for responders and partial responders (on placebo or baricitinib 1 mg) who are rescued to a higher dose (baricitinib 2 mg or baricitinib 4 mg). This censoring rule will be applied to all efficacy endpoints conducted for the responder, partial responder, and nonresponder mITT populations (defined in Section 6.2.1). For responders and partial responders, the censoring rule will censor efficacy data after permanent study drug discontinuation or rescue date, whichever occurs first. For nonresponders, the censoring rule will censor efficacy data after permanent study drug discontinuation.

The *Period 2 censoring rule* will censor efficacy data after permanent study drug discontinuation or after retreatment, whichever occurs first. This censoring rule will be applied to efficacy endpoints and safety conducted for the Period 2 population corresponding to the withdrawal and downtitration substudy.

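### In the withdrawal and downtitration substudy, the primary mLOCF can count a patient retreated for relapse as an EASI75 responder on placebo or the lower dose, and the planned NRI analysis does not isolate the effect

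*SAP*

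**What the plan says.** - **Trigger.** The notes to the study design figure (SAP Section 5.1; protocol addendum Section 4.3.1) say that substudy patients are retreated automatically when IGA is 3 or more. EASI plays no part.
- **Censoring.** SAP Section 6.4 lists "retreatment after downtitration or early withdrawal" as an intercurrent event. Its Period 2 rule "will censor efficacy data after permanent study drug discontinuation or after retreatment, whichever occurs first".
- **Imputation.** In Section 6.4.3, mLOCF "replaces missing data with the most recent nonmissing postbaseline assessment", and "data after an intercurrent event will not be carried forward thus the mLOCF is applied after the specified censoring rule is implemented". From the February 2021 lock, "mLOCF will be used as the primary analysis for all categorical endpoints (including PROs), and NRI will be used as sensitivity analysis". Section 6.11.1 repeats this, and Table JAHN.6.2 lists both methods for EASI75 in the substudy population.
- **Reason given.** Section 6.4.3 says mLOCF is reasonable because "data directly prior to an intercurrent event (such as initiation of rescue therapy or drop out) is likely a nonefficacious response". It prefers mLOCF to NRI because patients leave a long study for varied reasons.
- **Endpoint.** Section 4.2 lists, for all substudy patients, "Proportion of patients with a response of EASI75 from baseline of originating study assessed at 16 weeks after rerandomization (Week 68) and Week 104". Section 6.2.2 keeps the originating-study baseline for this endpoint in Period 2. Addendum patients, who have no originating study, use their JAHN baseline.
- **What relapse means.** Section 6.1 states: "Maintenance of treatment benefit is defined as response of IGA 0, 1, or 2". Section 4.2 describes retreated patients as having lost treatment benefit.

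**The concern.** Retreatment has one known cause: the investigator has recorded IGA 3 or more. The argument about mixed reasons for dropping out does not describe it. Yet the primary analysis carries the effect forward as if unchanged.

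For IGA the carried value is the trigger score, a nonresponse, if that score is an analysis value. EASI75 is a relative measure against a baseline before baricitinib treatment in most cases, so IGA 3 does not exclude it. The patient can then count as a responder in the randomized reduced-treatment arm while back on the original dose. The same patient may also count towards EASI75 within 16 weeks of retreatment, a separate secondary endpoint, and so appear both as retained and as recaptured response.

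The exploratory 4-point POEM and DLQI responses can behave likewise through Week 104. The 4-point itch response can do so only to Week 68, where its substudy analysis ends (Table JAHN.6.7).

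At stake is the substudy's stated purpose, which is to describe how response changes after withdrawal or downtitration. Section 6.2.3 compares the reduced arms with the continued dose.

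**Working it through.** **The plan's own figure.** The plan states no number for this rule. The one substudy figure with stated inputs is the addendum's contribution (protocol addendum Sections 4.4 and 4.8.1): 250 × 0.80 × 0.30 = 60, which agrees with the stated figure of about 60.

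**One patient traced through the written rules.** Illustrative values: baseline EASI 40; at Week 64 EASI 9.6 and IGA 3; retreated at Week 64.

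- Percent change at Week 64: 100 × (9.6 − 40) / 40 = −76, so EASI75 is met (limit 0.25 × 40 = 10).
- Data after Week 64 are censored.

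| Analysis | Week 64 | Weeks 68, 76, 84, 92, 104 |
|---|---|---|
| EASI75, mLOCF (primary) | responder | responder |
| EASI75, NRI (sensitivity) | responder | nonresponder |
| IGA 0, 1 or 2, mLOCF | nonresponder | nonresponder |
| IGA 0, 1 or 2, NRI | nonresponder | nonresponder |

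The IGA mLOCF row needs the Week 64 trigger score to be retained. If it is not, the earlier IGA of 2 or less is carried and the patient is an IGA (0,1,2) responder too. SAP Section 6.2.2 uses unscheduled assessments only within 4 days of a scheduled visit, in a rule written for Period 1. The fate of a trigger score from an unscheduled Period 2 visit is therefore not settled.

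**Room for overlap.** The EASI75 limit is 25% of baseline: 4 at baseline 16, 10 at 40, 16 at 64 and 18 at 72. At baseline 64 or more, a patient can be back at the addendum's entry threshold of EASI 16 and still be carried as a responder. At baseline 16 there is little room.

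**Size.** Excess in an arm = P(retreated) × P(EASI75 kept at relapse). Neither factor is in the documents. Assume 50% retreated on placebo, 25% on continued dose, and the same kept share q in both:

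| q | Placebo excess | Continued excess | Shrinkage of difference |
|---|---|---|---|
| 10% | 5 points | 2.5 points | 2.5 points |
| 20% | 10 | 5 | 5 |
| 30% | 15 | 7.5 | 7.5 |
| 40% | 20 | 10 | 10 |

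Two variations show how far this depends on the assumptions:

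- **Unequal kept shares.** With q of 10% on placebo and 30% on continued dose, the excesses are 0.50 × 10 = 5 and 0.25 × 30 = 7.5 points. The difference widens by 2.5.
- **No censoring at retreatment in the continued arm.** Only the placebo excess remains, and the shrinkage is 5 to 20 points.

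**In patients.** Of about 600 substudy patients (SAP Section 6.1), 1:1:1 allocation puts about 200 on placebo. At 50% retreated, 100 × 0.10 to 100 × 0.40 gives 10 to 40 placebo patients carried as EASI75 responders.

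**The case against.** The strongest reply is that the plan already shows the other answer. Table JAHN.6.5 runs substudy EASI75 under both NRI and mLOCF, and NRI counts retreated patients as nonresponders. This stands in part: the effect would show in the gap between the two results. But Section 6.4.1 also makes drop-outs and missed intermediate visits nonresponses, so the gap mixes three things.

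A second reply is that loss of benefit is captured by time to retreatment, relapse, rebound and the recapture endpoints, and that EASI75 need not duplicate an IGA-driven event. Carrying the last value is then an estimand choice. That is fair as far as it goes. The choice, however, rests on a reason that does not reach this event.

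Third, Section 6.4.3 says only that a poor prior value is likely, and the documents do not show how often IGA 3 and EASI75 coincide. This stands, and limits any claim about size.

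Fourth, the substudy was not sized to detect a difference and has no multiplicity control, POEM, DLQI and itch are exploratory, and data to Week 104 are already locked (SAP Section 3, Version 8). All of this stands. It limits what can be changed and how the result should be labelled.

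A reader might also infer that the difference between arms is certain to be compressed. The documents do not support that: it requires similar kept shares in the arms. The amount also depends on censoring in the continued arm. The Section 6.4 rule covers the whole substudy, yet its list of intercurrent events ties retreatment to downtitration or withdrawal, and the safety groups in Table JAHN.6.1 censor at retreatment only in the reduced arms.

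**Conclusion.** The concern holds as a defect of the written rule. No mLOCF provision makes a retreated patient an EASI75 nonresponder, so a relapse that ends randomized treatment can count as success in the primary analysis at Weeks 68 and 104. The reason in Section 6.4.3 is assured only for IGA, and only if the trigger assessment is retained. It would be wrong to read the IGA endpoints as safe in every case, or to extend the itch point past Week 68. After Week 104, EASI, POEM and DLQI are summarized on observed data, so carry-forward does not arise there.

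The size cannot be derived from the documents. The 2.5 to 10 points rest on assumed rates (50% and 25% retreated, 10% to 40% kept, equal shares, equal censoring), and the sign can reverse if the kept shares differ.

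Two limits apply. Main-protocol Sections 5.1.3.1 and 10, on which the addendum relies for retreatment and Period 2 analysis, were not available. Labels also differ within the SAP: Table JAHN.6.5 marks only Week 68 as secondary, while Section 4.2 also lists Week 104.

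This should be corrected, but it does not invalidate the substudy.

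**What to change.** In SAP Section 6.4.3 and Table JAHN.6.2, for categorical substudy endpoints through Week 104 (itch to Week 68):

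1. Count retreatment as nonresponse from the retreatment visit onward, and keep mLOCF for other missing data.
2. Report unmodified mLOCF and full NRI beside it, with the number of retreated patients in each arm whom mLOCF carries as EASI75 responders.
3. State whether the rule, and censoring at retreatment, apply equally in the continued-dose arm.
4. Label the analysis as added after lock, since data to Week 104 are already locked.

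Making retreatment itself a nonresponse also settles the IGA endpoints, whether or not the trigger score is kept as an analysis value.

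The cost is one added rule, a rerun of existing programs and a short table, with no new data. The downside is that response rates fall somewhat in every arm where retreatment occurs, and that a rule added after lock carries less weight than one fixed beforehand.

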4.1. Primary Objective

The primary objective of this study is to estimate the effect of long-term therapy with baricitinib on responders and partial responders at entry of Study I4V-MC-JAHN (JAHN) as assessed by the proportion of patients with a response of Investigator's Global Assessment (IGA) 0 or 1 at Weeks 16, 36, and 52.

In particular, the associated estimand for this objective is to measure the effect of long-term therapy with baricitinib on responders and partial responders at entry of Study JAHN as assessed by the proportion of patients with a response of IGA 0 or 1 at Weeks 16, 36, and 52 assuming that treatment response disappears after patients discontinue from study or treatment. See Sections 6.4.1 and 6.11.1 on how this estimand handles outcomes after the occurrence of any intercurrent event through nonresponder imputation (NRI).

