6.11.1. Primary Outcome and Methodology

The validated IGA for AD uses the clinical characteristics of erythema, papulation/induration, oozing/crusting, and lichenification to produce a single-item score ranging from 0 to 4. The primary analysis of the study is to estimate the effect of long-term therapy with baricitinib on responders and partial responders at the entry of Study JAHN by evaluating the proportion of patients with a response of IGA 0 or 1 assessed at Weeks 16, 36, and 52 using the mITT population, assuming that treatment response disappears after the patient is rescued or discontinued study or study treatment. This will serve as the primary estimand. In this estimand, missing data due to the application of the censoring rule and the occurrence of other noncensor intercurrent events will be imputed using the NRI method described in Section 6.4.1. A logistic regression analysis as described in Section 6.2.3 will be used for the comparisons. The odds ratio, the corresponding 95% CIs and p-value, as well as the treatment differences and the corresponding 95% CIs, will be reported.

For analyses on and after the February 2021 DBL, mLOCF will be used as Primary approach for all categorical endpoints (including PROs) and NRI will be used as supportive sensitivity.

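### mLOCF became the primary method from the February 2021 lock, but the composite primary estimand tied to NRI was not restated, so the primary IGA 0/1 rates no longer estimate the declared quantity

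*SAP*

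**What the plan says.** Section 4.1 of the SAP sets the primary estimand as the proportion with IGA 0 or 1 at Weeks 16, 36 and 52 among responders and partial responders, "assuming that treatment response disappears after patients discontinue from study or treatment", and refers to NRI as the way of handling intercurrent events. Section 6.11.1 repeats it with rescue added, "assuming that treatment response disappears after the patient is rescued or discontinued study or study treatment", calls this the primary estimand and again names NRI. Section 6.4.1 justifies NRI as a composite strategy.

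Section 6.4.3 changes the method: "mLOCF will be used as the Primary analysis in/after February 2021 DBL, as NRI may underestimate potential treatment effect in a long-term study". Footnote c of Table JAHN.6.2 and the closing paragraph of Section 6.11.1 say the same, and NRI becomes the sensitivity analysis for categorical endpoints. Section 6.4.3 describes the new method's premise: "The mLOCF assumes the effect of treatment remain the same after the event that caused missing data".

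In Table JAHN.6.5 the row marked primary for IGA 0/1 is the combination-therapy (JAIY) responders and partial responders, Weeks 0-52, summarised descriptively under both NRI and mLOCF.

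**The concern.** The declared estimand treats a patient who stops treatment as a nonresponder from then on. The method now labelled primary gives that patient the last status seen before stopping. These answer different questions, and Section 6.11.1 holds both, one paragraph after the other.

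The primary objective is to estimate a proportion, so the rate printed as primary is the main result. If it comes from mLOCF and the text beside it describes the composite estimand, a reader will take it as the share of patients who stayed on treatment and were responding at Week 52. It would also include patients who left while responding.

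**Working it through.** **Assumptions side by side.** Sections 4.1 and 6.11.1: response is lost after the event. Section 6.4.3: the effect is unchanged after it. No section of the SAP reconciles the two. The SAP does recognise the issue elsewhere: Section 6.4.2 says that "the MMRM imputation implies a different estimand (hypothetical strategy [ICH E9 R1]) than the one used for NRI on categorical outcomes". It makes no such statement for mLOCF.

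**Which results are affected.** Section 6.2.3 expects all monotherapy patients (JAHL, JAHM) to have reached Week 52 or discontinued by the December 2019 cutoff, before the switch. For JAIY responders and partial responders, Appendix 2 schedules IGA 0/1 at Weeks 0-24, and at Week 36 on the evaluable set, for the May 2020 lock, also before the switch. The mismatch therefore concerns the JAIY primary rates reported from February 2021 onward, and Week 52 in particular.

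**Direction.** Take N patients with a recorded baseline. R are observed responders at the visit, C are missing or censored patients whose carried value is a response, and M are patients whom mLOCF excludes for having no postbaseline value (all nonresponders under NRI).

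- NRI rate = R / N
- mLOCF rate = (R + C) / (N - M)

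Since C >= 0 and N - M <= N, the mLOCF rate is never below the NRI rate.

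**Size.** The plan gives no figure to reproduce and no dropout rate for this population. The nearest is Section 4.8.1 of the protocol addendum, which anticipates about 80% completion of 52 weeks in the open-label arm. Using 20% for JAIY patients is an assumption. Let d be the proportion missing or censored and s the share of those carrying a response. With nobody excluded, gap = d x s, in percentage points:

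| d | s = 0 | s = 10% | s = 20% | s = 40% |
|---|---|---|---|---|
| 5% | 0 | 0.5 | 1 | 2 |
| 10% | 0 | 1 | 2 | 4 |
| 20% | 0 | 2 | 4 | 8 |

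Example: with a response rate of 50% among those observed, d = 20% and s = 40%, NRI = 0.50 x 0.80 = 40.0% and mLOCF = 40.0% + 0.20 x 0.40 = 48.0%.

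**Denominator.** Section 6.4.1 says of NRI that "randomized patients without at least 1 postbaseline observation will be defined as nonresponders for all visits". Section 6.4.3 says "Analyses using mLOCF require a nonmissing baseline and at least 1 postbaseline measure otherwise the data is missing for analyses purposes". Whether this excludes anyone here is not settled. Under Section 6.2.2 the efficacy baseline for these patients is the originating-study value, so the IGA at JAHN entry may itself be postbaseline.

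- If it counts, nobody in this population is excluded for lack of a postbaseline value, and an early dropout's entry status is carried forward. For a responder at entry, that is a response.
- If it does not count, and 2% have no later value (assumed, within d = 20%), the gap at s = 0 is 0.80p x (1/0.98 - 1), where p is the response rate among those observed. This is 0.5 points at p = 30% and 1.0 at p = 60%, from the denominator alone.

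All these figures assume that the COVID-19 multiple imputation of Section 6.4.4 is not triggered. At the February 2021 lock it applies to IGA 0/1 if COVID-related missingness exceeds 5%.

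**The case against.** The best defence is that the change is disclosed with a reason, that Table JAHN.6.5 plans both methods for the primary row, and that NRI stays as a sensitivity analysis. The declared quantity will therefore still be computed. That is right, and it is why the fix is cheap. It does not resolve which rate is called primary, or what that rate is said to estimate.

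A second defence is that the gap may be small. Section 6.4.3 argues that the value just before an intercurrent event is probably not a good response, which would put s near zero. The same section justifies the switch by saying that NRI may understate the effect, which implies that s is not near zero. The text supports both ends of the range, so the size stays open. Rescue should add little: Section 6.4 limits rescue to a higher dose to placebo and 1 mg, Section 5.2 names no 1-mg arm for JAIY, and footnote a of Figure JAHN.5.1 links rescue with IGA of 3 or more, which would carry forward as a nonresponse. The full rescue rule is in the main protocol, which is not among the documents.

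Third, Section 4.1 speaks of discontinuation and not of a skipped visit, so a gap from missed visits is weaker evidence of mismatch with that section. Sections 6.4 and 6.11.1 do route missed visits to NRI.

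A reader might infer more than the documents support:

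- **Inflated differences between arms or false-positive risk.** The direction is fixed for each rate but not for a difference. Section 6.2.3 rules out formal comparisons with placebo in this population and Table JAHN.6.5 makes the row descriptive, although 6.11.1 still mentions logistic regression.
- **All primary results affected.** Monotherapy results, and JAIY Weeks 0-24 and part of Week 36, were scheduled before the switch.
- **The open-label addendum loses NRI.** Table APP.1.2 assigns NRI to its categorical endpoints, so the general wording of 6.4.3 is weak ground for that.

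**Conclusion.** The mismatch between estimand and estimator is real and rests on the text alone. From February 2021 the SAP labels as primary, for JAIY responders and partial responders, a rate that does not estimate the estimand it declares. Among patients with a recorded baseline that rate is equal to or higher than the declared one. The two coincide only if no carried value is a response and no nonresponder leaves the denominator.

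The size is uncertain: 0 to 8 points at 20% missing with carried-response shares of 0 to 40%, and 0 to 2 points at 5% missing. Both inputs are assumptions. Whether mLOCF also shrinks the denominator depends on an undefined point, the status of the JAHN-entry IGA, and should not be stated as fact. This should be fixed because it changes what the headline rate means. It does not invalidate the study.

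**What to change.** Preferred: in Sections 6.4.3 and 6.11.1 and Tables JAHN.6.2 and JAHN.6.5, present the NRI rate as the estimate of the declared primary estimand and mLOCF as supportive, and bring Section 6.11.3 into line.

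Alternative, if mLOCF stays primary because data to Week 104 are already locked (Revision History, Version 8): restate and justify the estimand in Sections 4.1 and 6.11.1, do not describe mLOCF results as estimating the composite estimand, and print the NRI rate beside each mLOCF rate.

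In either case, report with each mLOCF rate the number of carried-forward responders and the number of patients excluded, and state whether the JAHN-entry IGA can be carried forward.

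Cost: both analyses are already planned, so no new data or models are needed, and the counts add one or two rows per table. The preferred route changes the primary label after the lock, which the report should say, and the headline rate may be somewhat lower. The alternative is mostly wording, at the price of acknowledging that the estimand changed.
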